### **Conventional Physiotherapy and Rehabilitation Program**

The conventional physiotherapy and rehabilitation program includes the application of Transcutaneous Electrical Nerve Stimulation (TENS), cold pack, therapeutic ultrasound, Codman Exercises, Wand exercises, shoulder wheel exercises, finger ladder exercises, strengthening exercises with elastic band and capsule stretching.

**The Effectiveness of Game-Based Virtual Reality Approach in Patients with  
Subacromial Impingement Syndrome**

**Statistical Analysis Plan (SAP)**

**(Pages 6 – 7)**

**April 8, 2019**

## **Statistical Analysis Plan (SAP)**

The statistical program Statistical Package for Social Sciences (SPSS) Version 11.5 (SPSS Inc., Chicago, IL, USA) will be used in the data analysis of the study. The p value of  $p < 0.05$  will be considered to be statistically significant in the data analysis. The initial demographic characteristics (age, boy, body weight) of all patients included in the study will be calculated.

‘Shapiro-Wilks Test’ will be used to investigate the appropriateness of the variables to normal distribution. ‘t-test’ will be used to compare the parameters of normal distribution in order to investigate the efficacy studies before and after the treatment; ‘Wilcoxon Test ‘ will be used to compare the parameters that do not comply with normal distribution.

**The Effectiveness of Game-Based Virtual Reality Approach in Patients with  
Subacromial Impingement Syndrome**

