### **Hypothesis of the Study**

H0: Addition of game-based virtual reality exercises to the rehabilitation program in patients with subacromial impingement syndrome does not contribute positively in improving the effectiveness of upper extremity for pain, range of motion and disability

H1: Addition of game-based virtual reality exercises to the rehabilitation program in patients with subacromial impingement syndrome contribute positively in improving the effectiveness of upper extremity for pain, range of motion and disability.

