### **Randomization of the Study Groups**

Individuals with Subacromial Impingement Syndrome applying to Cadde Medical Center for treatment will be invited to participate in the study. Individuals who volunteered to participate and whom met the criteria for participation will be randomized with simple random sampling method and will be divided into two groups. In both groups participants will receive conventional physiotherapy and rehabilitation. In the study group, 10 minutes of exercises with the game-based virtual reality exercises will added to the conventional physiotherapy and rehabilitation methods

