### Evaluations

A Physiotherapist will applying the following evaluation parameters at the baseline, and at the end of 4-weeks treatment program, the same physiotherapist will be applying evaluation parameters. Primary outcome measures and applied evaluations are shown in Table 1.

**Table 1.** Primary outcome measures and evaluation methods

Primary Outcome Measures	Evaluation Methods
Range of Motion (ROM)	Goniometer
Pain	Visual Analogue Scale (VAS)
Disability	The Disabilities of the Arm, Shoulder and Hand (DASH) Questionnaire
Quality of Shoulder Function	Constant-Murley Score
Muscle Strength	Dynamometer
Pain Threshold	Algometer
Proprioception	Marmara Visual Auditory Joint Education Device (MarvaJED)
Kinesiophobia	Tampa Kinesiophobia Scale (TKS)
Satisfaction of the Treatment	Visual Analogue Scale (VAS)

The range of motion will be defined with ‘goniometer’, the pain with ‘Visual Analogue Scale (VAS)’, the disability with ‘The Disabilities of the Arm, Shoulder and Hand (DASH) Questionnaire’, the quality of shoulder function with ‘Constant- Murley Score’, the muscle strength with ‘dynamometer’, the pain threshold with algometer, the proprioception with

‘Marmara Visual Auditory Joint Education Device (MarvaJED)’, the kinesiophobia with ‘Tampa Kinesiophobia Scale (TKS), the satisfaction of the treatment with ‘Visual Analog Scale (VAS)’.

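### The SAP's only inferential device is p<0.05 from tests described as before/after comparisons; it plans no between-group estimate or confidence interval, so the amount VR adds is not a planned result

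*Combined protocol and SAP*

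**What the plan says.** The Hypothesis section poses a two-way choice about the added effect of VR. Under H0, adding VR "does not contribute positively in improving the effectiveness of upper extremity for pain, range of motion and disability"; under H1 it does. Neither hypothesis carries a margin or a smallest useful difference.

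The Randomization section creates two arms: patients "will be randomized with simple random sampling method and will be divided into two groups". Both arms receive conventional physiotherapy, and Group II also receives 10 minutes of VR exercises. Outcomes are measured at baseline and "at the end of 4-weeks treatment program". The Evaluations section states that "Primary outcome measures and applied evaluations are shown in Table 1"; that table lists nine outcomes, all labelled primary.

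The SAP section is short. It names the software, a threshold of p<0.05 that "will be considered to be statistically significant in the data analysis", baseline demographics and a Shapiro-Wilk check. The t-test is to be used for normally distributed variables "in order to investigate the efficacy studies before and after the treatment", and a Wilcoxon test "will be used to compare the parameters that do not comply with normal distribution". The SAP mentions no effect estimate, no interval and no reading of a non-significant result. Neither document gives a sample size or power.

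**The concern.** The trial asks how much VR adds to treatment that both arms receive. Answering that needs the difference between the arms, with a measure of its uncertainty. The SAP offers a p-value threshold and a description of change over time, and neither is that quantity.

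Two misreadings are left open. If a p-value for the group comparison is produced and is 0.05 or above, the wording of H0 invites the conclusion that VR has no benefit, even when the data are compatible with a useful one. If p is below 0.05, nothing planned shows whether the gain in VAS points, degrees or DASH points is large enough to matter. In both cases the reader would lack the figure needed to judge.

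**Working it through.** The plan gives no figure to reproduce: there is no sample size, SD, target effect, power or margin. The check is first a comparison of the sections, then an illustration.

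**Step 1. Does the planned analysis yield the quantity in the hypothesis?**
- Quantity needed (Hypothesis, Randomization): the Group II minus Group I difference in change, or in the 4-week value, for pain, range of motion and disability.
- Quantity planned (SAP): a t-test described as a before/after comparison, and a Wilcoxon test for non-normal variables. The clause on the Wilcoxon test does not say whether the paired or the two-sample version is meant.
- If the tests are paired within arms, their p-values concern change over time. Both arms receive active treatment, so such a p-value does not isolate the contribution of VR.
- If the tests are between arms, a p-value still gives neither the size of the difference nor its precision, and the SAP does not commit to reporting either.

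On either reading, the amount VR adds is not a planned result.

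**Step 2. Does anything limit how a non-significant p is interpreted?** The SAP says what counts as significant and is silent on p≥0.05. The Hypothesis section has no margin. Nothing in the documents prevents p≥0.05 from being reported as H0.

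**Step 3. How much could a null-looking result leave open?** Assumptions: n per arm of 15 to 40, equal arms, a common SD for the analysed quantity and a two-sided 95% interval.

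Half-width in SD units = t(0.975, 2n−2) × √(2/n)

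- n = 15: 2.048 × 0.3651 = 0.748
- n = 20: 2.024 × 0.3162 = 0.640
- n = 30: 2.002 × 0.2582 = 0.517
- n = 40: 1.991 × 0.2236 = 0.445

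At 30 per arm, an observed difference of exactly zero has an interval from −0.52 to +0.52 SD. An observed benefit of 0.2 SD has 0.2 ± 0.52, that is −0.32 to +0.72 SD. Both are non-significant, and neither excludes a benefit of half an SD. With larger arms the interval narrows, to about 0.35 SD at 64 per arm and 0.28 SD at 100. The documents give no SDs, so these figures cannot be turned into VAS points, degrees or DASH points.

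**The case against.** The strongest reply is that the plan never says p≥0.05 will be taken as proof of H0. That is correct. A reader might infer a rule in which p<0.05 selects H1 and anything else selects H0, but the SAP only defines significance and does not link the threshold to the hypotheses. H0 is worded as an ordinary null of no benefit, which does not commit the sponsor to accepting it. What stands is the narrower statement that the misreading is possible and nothing in the plan guards against it.

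A second reply is that the planned p-value may not compare the arms at all. A reader might treat it as a between-arm result, but the SAP does not clearly specify one. The lack of a clear between-group test is a separate and more basic problem. It does not remove this point, because it makes the absence of a between-group estimate more complete.

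A third temptation is to quote miss rates. With a true benefit of 0.5 SD and a two-sided test, p≥0.05 would occur about 74%, 66%, 52% and 40% of the time at 15, 20, 30 and 40 per arm. These figures depend on an assumed effect: at 30 per arm the rate is about 79% for 0.3 SD and 14% for 0.8 SD. They also depend on sidedness, which is not stated although H1 is directional. They describe power, which reporting an interval does not change, so they are not a measure of this defect.

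It may also be said that software prints an interval with a t-test anyway. The SAP does not commit to reporting it, and a rank-test p-value on its own gives no size of effect.

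**Conclusion.** The point holds as a gap in the planned analysis. As written, the SAP would not deliver the size of VR's added effect or its uncertainty for any of the nine outcomes, although that effect is the subject of the hypothesis. This rests on the text alone and needs no assumption about sample size.

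The consequence for a non-significant result is conditional: it could be reported as no benefit, but the documents do not say that it will be. Its size is illustrative only. With 15 to 40 per equal arm, intervals of about ±0.75 to ±0.45 SD would leave a moderate benefit open. Larger arms would leave less open, and the documents do not say which applies.

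**What to change.** In the SAP section, add wording to this effect:

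- For each outcome, report the Group II minus Group I difference in change from baseline (or in the 4-week value, with the choice stated in advance), in the outcome's own units, with a 95% confidence interval. Use the mean difference, or the Hodges-Lehmann shift where a two-sample rank test is used.
- Base the conclusion about VR on that difference and its interval.
- Report p≥0.05 as no difference shown, not as acceptance of H0.

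The data are already to be collected and no clinical procedure changes. The cost is modest but more than editorial: the between-group comparison has to be stated explicitly, and estimates are needed for nine outcomes, some with several components (pain during activity and at rest, and several shoulder and elbow movements). Some results will have to be reported as inconclusive.

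### The SAP lets a Shapiro-Wilk check on the variables choose the test without directing it to the paired differences or residuals, so the choice can be misdirected and, if made per arm, can differ between arms

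*Combined protocol and SAP*

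**What the plan says.** The section Statistical Analysis Plan (SAP) is the whole analysis plan. Its Shapiro-Wilk test "will be used to investigate the appropriateness of the variables to normal distribution". Where normality is accepted, a t-test is used "in order to investigate the efficacy studies before and after the treatment". Otherwise a Wilcoxon test "will be used to compare the parameters that do not comply with normal distribution". A p-value below 0.05 "will be considered to be statistically significant in the data analysis".

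The SAP does not say:
- whether the quantity checked is a measured score, a change or a model residual;
- whether the check is run per arm, per time point or pooled, or what happens if the checks disagree;
- whether the t-test is paired, or which Wilcoxon test is meant.

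The protocol supplies the setting. Participants "will be randomized with simple random sampling method and will be divided into two groups" (Randomization of the Study Groups). They are assessed "at the baseline, and at the end of 4-weeks treatment program" (Evaluations). Table 1 lists nine primary outcomes. The alternative hypothesis is about the added effect of the virtual reality exercises (Hypothesis of the Study), which is a comparison between arms.

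**The concern.** A paired t-test assumes that the before-to-after differences are roughly normal. It assumes nothing about the shape of the baseline and 4-week scores taken separately. Skewed scores can have normal differences, and near-normal scores can have skewed differences. A check on the scores therefore looks at a quantity that does not govern the test it selects.

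The choice is also made from the data. If it is made within each arm, one arm may be summarised by means and the other by ranks for the same outcome. At stake are a predictable method for each primary outcome, a consistent presentation of the two arms and, to a lesser degree, power.

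**Working it through.** The plan gives no sample size, power, SD or effect size, so there is no figure of its own to reproduce.

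**Inputs.** From the documents: two arms, two time points, significance at 0.05, nine outcomes in Table 1. The satisfaction form in Annex 2 exists only for the end of treatment, so 9 − 1 = 8 outcomes can have a before/after test. Assumed: Shapiro-Wilk at 0.05, two-sided paired tests, 15, 20 or 30 per arm in equal groups, pre/post correlation 0.6, within-arm shift 0.5 SD, between-arm difference 0.6 SD. Simulations used 4,000 to 6,000 runs per setting, so the standard error of one proportion is at most √(0.25/4000) = 0.008.

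**1. Different tests in the two arms, all data truly normal.** Let q be the chance that an arm is sent to Wilcoxon. The arms then differ with probability 2q(1 − q).
- One check per arm: q = 0.05, so 2 × 0.05 × 0.95 = 9.5%.
- Baseline and 4-week values both checked: q = 1 − 0.95² = 0.0975, so 2 × 0.0975 × 0.9025 = 17.6% (simulated 18%).
- One pooled check per outcome: 0%.

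At least one split among eight independent outcomes: 1 − (1 − 0.095)⁸ = 55%, or 1 − (1 − 0.176)⁸ = 79%.

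**2. Does a check on scores pick the same test as a check on the change?** The scores check covers both time points.

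| Simulated setting | Choices disagree, n = 15 / 20 / 30 | Arms differ under scores check |
|---|---|---|
| All normal | 14% / 14% / 14% | 18% / 18% / 18% |
| Scores skewed, change normal | 52% / 67% / 85% | 50% / 44% / 21% |
| Bounded 0–10 scale | 36% / 45% / 64% | 43% / 49% / 44% |

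In the second row the change is normal, yet the scores check picks the t-test in only 48% / 31% / 12% of arms. A check on the change picks it in 94% to 96%.

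**3. Power cost of the gate when the change is normal** (n = 15 / 20 / 30).
- Within arm, normal scores: paired t-test 0.523 / 0.655 / 0.838; gate 0.521 / 0.654 / 0.837. Loss 0.1 to 0.2 points.
- Within arm, skewed scores: 0.513 / 0.660 / 0.846 against 0.507 / 0.644 / 0.831. Loss 0.6 to 1.6 points.
- Between arms, t-test on change against a gated choice of t-test or rank-sum on change: loss 0.4 to 0.7 points with normal scores and 2.1 to 2.8 with skewed scores.
- With no effect, the gate rejected in 0.043 to 0.057 of runs.

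**4. What the proposed analysis gains.** With normal data, ANCOVA has power 0.49 / 0.63 / 0.81 against 0.41 / 0.54 / 0.72 for the gated choice on change. An ungated t-test on change has 0.42 / 0.55 / 0.72, so nearly all the gain is baseline adjustment. The ratio of error variances, ANCOVA to change score, is (1 − 0.6²) / (2(1 − 0.6)) = 0.64 / 0.80 = 0.8. The gain is not universal. In the setting with skewed scores and normal change, ANCOVA had 0.413 / 0.532 / 0.720, slightly below the t-test on change (0.428 / 0.542 / 0.729) and 1.1 to 1.6 points above the gate (0.400 / 0.521 / 0.704).

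**The case against.** **The wording is open.** A change score is also a variable, and the SAP sorts each parameter as normal or not, which could mean one classification and one test per outcome. This stands as far as it goes. Neither a check on the measured scores nor a check per arm is written. The first is the natural reading, because the protocol describes only scores at two visits and the SAP never mentions differences. The second is possible because before/after tests in a two-arm trial are usually run within arms. A split between arms is therefore conditional.

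**Independence is doubtful.** The Constant-Murley form itself covers pain, range of motion and strength, which are separate rows of Table 1. The 55% to 79% is an illustration. A reader who counts all nine rows would get about 82% from 1 − (1 − 0.176)⁹, but satisfaction has no baseline value and does not belong in the count.

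**Power.** A reader might infer a large loss, because one can be constructed. With a normal baseline of SD 10, a change following a t distribution with 2 df and a shift of 0.9, the scores gate has power 55.1% against 70.0% for a gate on differences at n = 20, and 68.4% against 86.2% at n = 30. This needs a pre/post correlation near 0.98 and a change with infinite variance. With baseline SD 1 the gap is about 3 points (66.7% against 69.4%; 83.9% against 86.8%). With 5 df it is 2 to 4 points even at correlation 0.99. With the 2-df change limited to ±3 before the shift, as bounded scales would impose, the gap vanishes (75.7% against 75.8% at n = 20). The documents do not support a loss of 15 points or more as the expected cost.

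**The larger gap lies elsewhere.** The SAP names no between-arm test, and within-arm p-values do not answer the hypothesis under any normality rule. This also stands, and it is why the fix goes beyond moving the check.

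**Conclusion.** The concern holds in a limited form. The test for each before/after comparison depends on a normality check that the SAP does not direct to the differences or residuals and, on its plain reading, applies to the measured scores. The choice of test can be misdirected. If the check is made per arm, the arms can receive different tests for 9.5% to 18% of outcomes under normality, and for 21% to 50% in the skewed and bounded settings simulated.

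The cost in power is small, typically about 0 to 3 points, and larger only for an extreme heavy-tailed change. All these figures rest on the assumed sample sizes, correlation, effects and distributions. A reader might also infer a raised false-positive rate. The simulations with normal change do not show one, and none is claimed. When the change was skewed, rejection at zero mean change exceeded 0.05 even for an ungated t-test (0.082 to 0.088), so that excess cannot be put down to the gate alone.

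The SAP should be changed, mainly so that one known method applies to each primary outcome and answers the between-arm question.

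**What to change.** 1. Delete the Shapiro-Wilk gate.
2. Prespecify one between-arm analysis per outcome: an ANCOVA of the 4-week value on group and baseline. For satisfaction, collected only after treatment, use a between-group comparison without baseline.
3. Check model residuals as a diagnostic only, with no switch of method.
4. Add a rank-based sensitivity analysis, reported whatever the residuals show: for example Mann-Whitney on change, or on the score itself for satisfaction.
5. Treat any within-arm before/after test as descriptive. Use the same named test in both arms, with normality judged on the 4-week-minus-baseline differences.

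Moving the Shapiro-Wilk test to the change and keeping the gate would not be enough. Run per arm with normal change, it still split the arms in about 9% to 11% of outcomes.

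The cost is SAP wording and a little more analysis. No new data, participants or software are needed.

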### **Treatment Program**

The participants in the study will be rehabilitated in Cadde Medical Center for 5 times a week for 4 weeks, a total of 20 sessions (Duration of one session is 60 minutes).

Group I (Control Group) will receive conventional physiotherapy and rehabilitation treatment program

Group II (Study Group) will receive conventional physiotherapy and rehabilitation treatment program and game-based virtual reality exercises (with a device named USE-IT) (10 minutes).

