### Assessment of satisfaction after the treatment

- How satisfied are you with the decrease of pain at the end of treatment?

0.....5.....10  
(Not satisfied at all) (Very satisfied)

- How satisfied are you with your functionality at the end of treatment?

0.....5.....10  
(Not satisfied at all) (Very satisfied)

- How satisfied are you with all of your treatment?

0.....5.....10  
(Not satisfied at all) (Very satisfied)

- How satisfied are you with your physiotherapist?

0.....5.....10  
(Not satisfied at all) (Very satisfied)

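### The SAP plans no comparison of Group II with Group I; its only stated efficacy comparison is before versus after treatment, so the trial's hypothesis has no planned test

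*Combined protocol and SAP*

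**What the plan says.** The research question is comparative. Under Hypothesis of the Study, H1 reads "Addition of game-based virtual reality exercises to the rehabilitation program in patients with subacromial impingement syndrome contribute positively in improving the effectiveness" for pain, range of motion and disability; H0 is its negation.

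The design matches that question. Under Randomization of the Study Groups, patients are allocated at random to two groups, and "In both groups participants will receive conventional physiotherapy and rehabilitation". Under Treatment Program, "Group I (Control Group) will receive conventional physiotherapy and rehabilitation treatment program", while Group II receives the same programme plus 10 minutes of VR exercises. Under Evaluations, "A Physiotherapist will applying the following evaluation parameters at the baseline, and at the end of 4-weeks treatment program" the outcomes are measured, so there are two time points.

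The SAP names the software, a significance level of 0.05, calculation of demographics for all patients, and a Shapiro-Wilk check. It then gives its efficacy analysis: a t-test "will be used to compare the parameters of normal distribution in order to investigate the efficacy studies before and after the treatment", and a Wilcoxon test that "will be used to compare the parameters that do not comply with normal distribution".

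Table 1 lists satisfaction among the primary outcomes. Its form in Annex 2 is set at the end of treatment only, for example "How satisfied are you with the decrease of pain at the end of treatment".

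**The concern.** The hypothesis concerns the difference between two randomised groups, but the only comparison the SAP describes is between two time points. Both arms receive a multi-component physiotherapy programme in 20 sessions, so improvement from baseline is expected in both whether or not VR does anything. A before/after test in Group II combines the effect of conventional treatment, natural recovery, regression to the mean and any VR effect, and cannot separate them.

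Two things are at stake. Followed as written, the plan never tests H0, so the randomisation goes unused. The SAP also has no rule for moving from before/after results to a conclusion about VR, so that step would be chosen after the data are seen.

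**Working it through.** **Step 1: what the hypothesis needs and what the SAP supplies.**

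| Needed to test H0 | In the SAP |
|---|---|
| A contrast of Group II with Group I | Not mentioned; the SAP text does not refer to groups or to a control |
| A quantity to compare (change, or 4-week value adjusted for baseline) | Only before versus after treatment |
| A two-sample test or model | A t-test or Wilcoxon test, not identified as paired or independent, per arm or pooled |
| An estimate with a confidence interval | None |
| An analysis for satisfaction | None that can be run: it has no baseline value |

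No other section reviewed supplies the missing items.

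**Step 2: inputs for an illustration.** The documents give no sample size, SD, correlation or expected change, so there is no figure of the plan's own to reproduce. Assumed: n = 20 per arm (range 15 to 30), baseline-to-4-week correlation ρ = 0.5 (range 0.3 to 0.7), normal data, and a two-sided 0.05 level (the SAP gives 0.05 but not the sidedness). Improvements d are in units of the outcome SD.

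**Step 3: no VR effect, both arms improve by d.** The SD of change is √(2(1−ρ)), which is 1 at ρ = 0.5. The power p of a paired t-test comes from the noncentral t distribution with n−1 degrees of freedom and noncentrality d√n / √(2(1−ρ)). For example, n = 20 and d = 1.0 give noncentrality 1.0 × √20 = 4.47 and p = 0.989.

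If a reader declared success when Group II was significant and Group I was not (a rule the SAP does not state), the probability with independent arms and equal true change is p(1−p). This cannot exceed 0.25.

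| d (SD) | p, n=15 | p, n=20 | p, n=30 | p(1−p), n=15 | p(1−p), n=20 | p(1−p), n=30 |
|---|---|---|---|---|---|---|
| 0.3 | 0.192 | 0.247 | 0.355 | 0.155 | 0.186 | 0.229 |
| 0.45 | 0.368 | 0.480 | 0.664 | 0.233 | 0.250 | 0.223 |
| 0.6 | 0.580 | 0.721 | 0.888 | 0.244 | 0.201 | 0.099 |
| 0.8 | 0.821 | 0.924 | 0.988 | 0.147 | 0.070 | 0.011 |
| 1.0 | 0.949 | 0.989 | >0.999 | 0.048 | 0.011 | <0.001 |

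At n = 20 and d = 1.0, p is 0.948 for ρ = 0.3 and above 0.999 for ρ = 0.7. In simulation (20,000 runs, n = 20, ρ = 0.5), the between-group tests rejected at close to the nominal rate across all these improvements: 0.048 to 0.051 for ANCOVA and 0.048 to 0.050 for a t-test on change.

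**Step 4: VR truly adds 0.8 SD (control improves 1.0 SD, VR arm 1.8 SD), n = 20.** At ρ = 0.5 both arms' before/after tests are significant in 0.989 of runs. With no VR effect and d = 1.0, both are significant with probability 0.989² = 0.978. The before/after results therefore look much the same whether VR works or not. Power of the between-group tests:

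| ρ | ANCOVA | t-test on change | Mann-Whitney on change |
|---|---|---|---|
| 0.3 | 0.728 | 0.552 | 0.526 |
| 0.5 | 0.802 | 0.691 | 0.667 |
| 0.7 | 0.926 | 0.892 | 0.872 |

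**The case against.** The strongest defence is that a between-group test was meant. The SAP sentence is loosely worded and never says paired or within-group. It could be read as comparing the groups on variables measured before and after treatment. The Wilcoxon clause does not repeat the before/after phrase, and that name covers both the signed-rank and the rank-sum test. A comparative hypothesis, a randomised control group and an outcome measured only once all suggest that a two-sample analysis was in mind.

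That intent is plausible, but it is not stated. The only contrast the text describes is before versus after; the tests are not identified as two-sample, and the quantity to be analysed is not named. A plan whose central comparison must be inferred does not fix it in advance.

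A second objection is that some pages between the SAP and Annex 2 were not available for this review. The SAP text reads as complete and does not point to further analysis text, but the statement of absence covers only the pages seen.

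Third, every numerical input is assumed, and the rule behind p(1−p) is not the sponsor's; at large improvements it gives figures below 5%. This stands as a limit on the numbers. The conclusion does not depend on them, because a within-arm test does not test a between-arm hypothesis at any sample size. Likewise, the power advantage of ANCOVA supports a choice of method and is not evidence of the defect.

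**Conclusion.** The concern holds, and it must be fixed before analysis. As written, the SAP gives no test of H0, and for satisfaction the comparison it describes is impossible. This rests on the text alone.

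The size is illustrative. With 20 per arm, correlation 0.5 and no VR effect, the VR arm's before/after test is significant in 25% to 99% of trials for improvements of 0.3 to 1.0 SD, against about 5% for a between-group test. With a true added effect of 0.8 SD over a 1.0 SD control improvement, before/after tests are significant in both arms 99% of the time and do not reveal the effect, while ANCOVA detects it with 80% power (73% to 93% for correlations of 0.3 to 0.7). The actual rates depend on a sample size, SD and correlation that the documents do not give.

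**What to change.** State in the SAP that efficacy is assessed by comparing Group II with Group I, with patients analysed in the group to which they were randomised.

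- **Outcomes with a baseline:** ANCOVA of the 4-week value on group, with the baseline value as covariate. Report the adjusted Group II minus Group I difference with 95% CI and p-value. An independent-samples t-test or Mann-Whitney test on change would also cure the defect; ANCOVA is preferred for efficiency, and a rank-based test on change can serve as a sensitivity analysis.
- **Satisfaction:** compare the groups directly at 4 weeks by t-test or Mann-Whitney test, with the difference and 95% CI.
- **Before/after changes within each arm:** report descriptively only.

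Table 1 lists nine primary outcomes, so a multiplicity rule or a single named primary outcome is also needed. That is a separate point which this change does not settle.

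The cost is SAP wording, provided it is done before the data are analysed. No visits or measurements are added. Whether the trial is large enough for the between-group test cannot be judged, because no sample size is given.
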